13 QUALITY CONTROL AND QUALITY ASSURANCE

Quality Management (QM) measures will occur throughout this study to ensure adherence to protocol and collection of complete and accurate data. QM activities include those measures done as part of daily standard operating procedures by staff at each site and by the data management controls built into the PREDICT REDCap. QM activities will include activities undertaken at defined intervals to ensure that all study personnel have undergone training prior to initiating the protocol, QM activities are occurring, and study-related documents are up-to-date.

Staff Training

Training of all staff will be conducted and recorded in training logs. Each staff member has been identified by role. Records of completed training will be maintained by the node coordinator on the NCC Hub.

Training Modules	Who Will be Trained
Human Subjects, HIPAA	
• All Study Personnel
General Clinical Research Training (Human Subjects, HIPAA)	
• PI, Chief of Clinical Protocol, PBRN practitioners and designated investigators
General Overall (Study Purpose, Goals and Protocol)	
• All Study Personnel
REDCap System Training	
• National Dental PBRN Practitioners and Designated Investigators

Daily Operating Procedures

The PI and the Chief of Clinical Protocol will follow the REDCap dashboard to ensure compliance with study procedures. The dashboard exhibits red indicators for instruments which have been started and not completed, yellow indicators for instruments which have been completed and not verified and green indicators for instruments which have been completed and reviewed. The PI or Chief of Clinical Protocol will be responsible for reviewing each instrument and changing the status from unverified to verified. Any issues with compliance with the study protocol identified by the PI or Chief of Clinical Protocol will be reviewed with the National Dental PBRN Practitioner and be used to identify any unanticipated problems and develop/implement any necessary corrective action plans.

Subject Completion Review

As this is a feasibility study, reviews of surveys and case reports to ensure completeness will not be completed, rather the number/percentage of incomplete surveys and forms will be analyzed as an outcome measure. Consent forms will be reviewed for completeness at the mid-study visit for DHCW subjects and as part of the end-of-visit survey for patient subjects.

Data Management Controls

REDCap is a rich system which enables privileging, required data element entry and required data validation to be embedded into daily operations.

- **Privileging:** Every study staff member will be assigned a role which carries specific read/write/edit/delete privileges. Staff member will be assigned a role providing minimal rights sufficient to perform his/her responsibilities.
- **Structured Data:** Whenever possible, data will be collected via structured data responses rather than free-text. Structured data requires a respondent to check a valid response.
- **Data Validation:** Data fields will be established limiting responses to those that are reasonable. For example, year of birth would have a range of 2002 (corresponding to age 18 – the youngest

eligible) to 1920 (corresponding to age 100 – more than sufficient to cover the age range of individuals having impacted 3rd molars extracted.)

- **Required Fields:** Whenever appropriate, fields have been made required so as to ensure completed forms and questionnaires.

Structured responses are required for the CRFs so only valid responses can be recorded. In addition, REDCap has been programmed with all responses being required at time of completion which will trigger an error message, but subjects can save their responses without all responses being completed. Validation rules are employed where possible.

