The PRBN Node Research Coordinator will recruit PBRN dentist members to participate in the protocol. The PBRN Node Research Coordinator will contact PBRN dentist members to introduce the study and gauge initial interest. The dental office will be enlisted if the PBRN dentist member and 4-9 additional office DHCWs of the practice are willing to participate and the PBRN member is willing to perform the responsibilities of the protocol including enrolling and completing 10 patients. The PBRN practitioner's preference will determine which protocol (POC or LAB) will be followed in the office. In total, two POC offices will participate, and two LAB offices will participate.

Office	Study Group	Protocol	COVID-19 Related Tests (Method)
POC	1- DHCW in POC Offices	POC DHCW Protocol	
• Antigen (nasal swab)• Antibody (capillary blood)
	2- Patients in POC Offices	POC Patient Protocol	
• Antigen (nasal swab)
LAB	3- DHCW in Lab Offices	LAB DHCW Protocol	
• Virus (saliva and/or tongue)• Antibody (capillary blood)
	4- Patients in LAB Offices	LAB Patient Protocol	
• Virus (saliva)

Retention: In order to minimize loss of study participants and/or incomplete data collection, the following activities will take place:

- Node Coordinators will work with National Dental PBRN study participants responsible for recruiting subjects and completing surveys to encourage patient enrollment and study completion.
- Participants will receive compensation.

Compensation and Scheduled Payments: DHCWs who complete the study procedures including the end-of-study survey will receive \$125 each. Patients who complete the LAB study procedures including the post-visit survey will be provided \$100 and patients who complete the POC study procedures including the post-visit survey will be provided \$50.

Additional Plans to Minimize Missing or Incomplete Data: The following will minimize missing or incomplete data:

- When appropriate, REDCap survey data fields are set to "required".
- REDCap validation rules on data fields to limit responses to those which are valid

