- unexpected in terms of nature, severity, or frequency given (a) the research procedures that are described in the protocol-related documents, such as the sIRB-approved research protocol and informed consent document; and (b) the characteristics of the subject population being studied;
- related or possibly related to participation in the research (“possibly related” means there is a reasonable possibility that the incident, experience, or outcome may have been caused by the procedures involved in the research); and
- suggests that the research places subjects or others at a greater risk of harm (including physical, psychological, economic, or social harm) than was previously known or recognized.

8.1.2 *Serious Adverse Events*

A serious adverse event (SAE) is one that meets one or more of the following criteria:

- Results in death
- Is life-threatening (places the subject at immediate risk of death from the event as it occurred)
- Results in inpatient hospitalization or prolongation of existing hospitalization
- Results in a persistent or significant disability or incapacity
- Results in a congenital anomaly or birth defect
- An important medical event that may not result in death, be life threatening, or require hospitalization may be considered an SAE when, based upon appropriate medical judgment, the event may jeopardize the subject and may require medical or surgical intervention to prevent one of the outcomes listed in this definition.

If a SAE becomes known, the National Dental PBRN Practitioner or designated investigator will immediately notify the National Dental PBRN Node Coordinator who will then notify study PI. The National Dental PBRN Node Coordinator will record the event in the REDCap Unanticipated Problem form and Serious Adverse Event Form based upon information obtained.

8.1.3 *Protocol Deviations/Violations*

As the purpose of this pilot is to determine if the study windows are appropriate, activities taking place outside of a specified window will not be considered a protocol deviation or violation. In addition, any missed or incomplete surveys or forms will not be considered protocol deviation or violation as these are outcome measures for the pilot study.

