11.1 Final Analysis Plan

Data to be collected includes:

Item	Type of Variable
Willingness to Participate 
• Dentist, Hygienist, Assistant and Front Desk personnel willing to participate• Patient willingness to participate	
• Willingness to participate (Binary – Yes/No)
Triage Survey	
• Ease of Administration (3 point Likert Scale)
◦ Very easy to complete survey due to administration method◦ Easy to administer complete survey due to administration method◦ Not easy to complete survey due to survey administration method• Completeness (Binary – Yes/No)• Question understandability (3 point Likert Scale)
◦ Very clear to understand◦ Understandable with some clarification provided by the administrator◦ Not clear to understand
Safety Perception Survey 
• Start-of-Study DHCW Survey• End-of-Study DHCW Survey• Start-of-Visit Patient Survey• End-of-Visit Patient Survey	
• Administration method (3 point Likert Scale)
◦ Very easy to complete survey due to administration method◦ Easy to complete survey due to administration method◦ Not easy to complete survey due to administration method• Completeness (Binary – Yes/No)• Question understandability (3 point Likert Scale)
◦ Very clear to understand◦ Understandable with some clarification provided by the administrator◦ Not clear to understand

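### Does the plan need a written rule for when a survey with blanks, or one never opened, counts as complete?

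*Combined protocol and SAP*

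**What the plan says.** Section 13 (Subject Completion Review) says that surveys and case reports will not be reviewed for completeness; "rather the number/percentage of incomplete surveys and forms will be analyzed as an outcome measure". Under Data Management Controls it adds that "REDCap has been programmed with all responses being required at time of completion", that a blank triggers an error message, and that "subjects can save their responses without all responses being completed". The same list says: "Whenever appropriate, fields have been made required so as to ensure completed forms and questionnaires". Section 5.3 carries a similar qualifier: "When appropriate, REDCap survey data fields are set to" required status.

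Section 11.1 lists the variable as "Completeness (Binary – Yes/No" for the triage survey, the safety perception surveys and the testing case report. Frequencies are the only analysis. Section 3.0 has two related measures: the share of participants who complete the surveys, and the share of surveys completed.

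Section 8.1.3 says that "any missed or incomplete surveys or forms will not be considered protocol deviation or violation as these are outcome measures for the pilot study". On the monitoring side, Section 13 (Daily Operating Procedures) says: "The dashboard exhibits red indicators for instruments which have been started and not completed". It gives other colours for completed instruments, before and after verification, and none for an instrument never opened.

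**The concern.** Completeness is a feasibility outcome and is meant to guide refinement of the REDCap instruments. The software allows a partly blank survey, so such surveys may occur, yet the plan has no sentence scoring them. Nor does it say whether a survey never opened stays in the denominator. The required-field statements differ as well: some fields in two places, all responses in another.

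The worry is that two analysts could report different percentages from the same data, and that a reader could not tell which rule was used. There is also a knock-on point. The safety culture score in Section 3.1 sums six items, so if any saved survey counted as complete, one with a missing item could be reported as complete although its sum is short.

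**Working it through.** The plan states no completeness figure, so there is nothing to reproduce. The check is what the text implies for each open case, and then how much the answer could move.

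**1. Partly blank surveys.** Section 13 describes these as saved without every response completed, and in the same section makes incomplete surveys the outcome. The direct reading is that any blank means No. No sentence supports Yes.

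**2. Surveys never opened.** One Section 3.0 measure is a percentage of people, listed for both DHCWs and patients. Someone who never opened a survey has not completed it. Section 8.1.3 names missed surveys alongside incomplete ones as outcome measures, which argues against dropping them. The missing dashboard colour decides nothing, because the dashboard serves compliance monitoring and does not define the outcome.

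**3. Which fields count.** The difference between some fields and all responses matters only if Yes is taken to mean that all required fields are answered. The wording in step 1 refers to all responses. The difference reads as loose drafting, and the form set-up shows which fields were required.

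**4. Weight of one survey.** Targets are 40 DHCWs and 80 patients (Section 5.3).
- DHCWs: 1/40 = 2.5 points. Patients: 1/80 = 1.25 points.
- At the minimum of 5 consenting DHCWs in each of 4 offices: 4 × 5 = 20, and 1/20 = 5 points.
- Offices must be willing to enrol and complete 10 patients each: 4 × 10 = 40, and 1/40 = 2.5 points. This is a commitment asked of the office, not a floor on the number analysed.

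**5. Spread across readings.** The counts of surveys never opened and partly blank are assumed; the documents give none. There are 40 surveys due.

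| Reading | 2 never opened, 2 partly blank | 4 never opened, 4 partly blank |
|---|---|---|
| Blank = No, never opened = No | 36/40 = 90% | 32/40 = 80% |
| Blank = No, never opened excluded | 36/38 = 94.7% | 32/36 = 88.9% |
| Blank = Yes, never opened = No | 38/40 = 95% | 36/40 = 90% |
| Blank = Yes, never opened excluded | 38/38 = 100% | 36/36 = 100% |

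Steps 1 and 2 select the first row. The second row sets aside the per-person measure and Section 8.1.3, the third sets aside Section 13, and the fourth sets aside all of them.

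**6. What the text leaves open.** Section 7 (Reporting and Notification) says that patients positive on test or triage are not seen for the scheduled visit, so they may never be offered an End-of-Visit Survey. Section 5.4.2 says withdrawals are not replaced. Whether a form was due from these people is not stated. If one of 80 patients is not seen and the other 79 complete the survey, the choice is 79/80 = 98.75% or 79/79 = 100%, a difference of 1.25 points.

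**The case for a change.** The strongest case for a change is that frequencies are the whole analysis here, so a frequency without a written rule is a real omission. A natural reading is still not a rule, and it does not settle the denominator. The design itself produces the awkward cases: patients turned away and participants who withdraw. A few sentences would close the gap without any new data field, and reporting never opened, partly blank and fully answered surveys separately would let readers derive any version.

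Part of this stands. The definition is not written down, and step 6 is open on the text. But a bare instruction to use all forms due as the denominator would not settle step 6 either, because the question there is whether the form was due. The safety-culture point carries little weight. It needs the reading in which a blank counts as Yes, and Section 3.1 labels that score a full-study outcome, collected here to check the instrument; it is not among the Section 11.1 variables. Section 16 also commits to sharing de-identified data with a data dictionary, so completeness could be recalculated under another rule wherever blanks are visible.

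**Conclusion.** No change to the plan follows. This is missing detail that an analyst fills sensibly, because the text already points to No for a partly blank survey and No for one never opened. Nothing in the plan states a wrong rule, and a written rule would most likely record the reading an analyst would adopt anyway.

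The stakes are small. There is no sample size calculation, hypothesis test or completeness threshold, and one survey is worth 2.5 points among 40 DHCWs or 1.25 points among 80 patients. The wider spreads in the table depend on assumed counts and on readings that the text does not support.

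The conclusion assumes that the analyst follows the plain wording of Sections 3.0, 8.1.3 and 13, and that the report states the denominator used for patients not seen and for withdrawals, as a descriptive table normally does. If many patients were turned away, the treatment of their End-of-Visit Surveys would matter more, but it would still be a matter of labelling a frequency.

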7 STUDY PROCEDURES/EVALUATIONS

In general, the study will include completion of COVID-19 triage case reports, completion of COVID-19 testing, and administration of perception and attitude surveys. The DHCW Start-of-Visit, Mid-Visit and End-of-Visit and the Patient Start-of-Visit triage case report will include recording of temperatures and pulse oximeter reading for participants in both POC and LAB offices. During day 1, the dental visit, normal patient care will be provided to the patient subject.

Group 1- DHCWs in POC Office

Consent Process for Group 1- DHCWs in POC Offices

Within 4 weeks prior to study initiation in the dental office, the National Dental PBRN Node Coordinator will consent the DHCWs in the participating office. The consent will clearly outline participant expectations and offer the opportunity for potential participants to contact the National Dental PBRN Node Coordinator for more information as needed. DHCWs who elect to participate will affirm their willingness to participate by signing the consent form.

Study Procedures for Group 1- DHCWs in POC Offices

Prior to study initiation (Up to 4 weeks prior)

- Complete consent for all DHCW participants

Day 1

- Complete an electronic survey: *DHCW Start of Study Survey*
 - Questions include demographics, PPE used in the office, work practice controls used in the office, importance of triage and testing, importance of PPE measures, perceptions of safety and comfort in the workplace, safety culture in the office, SARS-CoV-2 testing preferences, dentists' role in SARS-CoV-2 testing, and willingness to test in the office
- Undergo a three-part COVID-19 triage screening*
 - Symptom questions
 - Presence or absence of:
 - fever or chills
 - cough
 - shortness of breath or difficulty breathing
 - fatigue
 - muscle and body aches
 - headache
 - loss of taste
 - loss of smell
 - sore throat
 - congestion or runny nose
 - nausea or vomiting
 - diarrhea
 - Temperature check
 - Pulse oximeter reading
- Complete two COVID-19 related tests**
 - SARS-CoV-2 POC test (administered by the PBRN practitioner or designated investigator)
 - A nasal swab will be swept inside the participant's nose (not beyond the nares) to collect the specimen for the SARS-CoV-2 test
 - The office staff will process the specimen in the dental office
 - ELISA Antibody test (specimen collected by the PBRN practitioner, designated investigator or self)

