14.3 Informed Consent Process

Informed consent is a process that is initiated prior to the individual agreeing to participate in the study and continues throughout study participation. Extensive discussion of risks and possible benefits of study participation will be provided to participants and their families, if applicable. A consent form describing in detail the study procedures and risks will be given to the participant. Consent forms will be sIRB-approved, and the participant is required to read and review the document or have the document read to him or her. The investigator or their investigator designee will explain the research study to the participant and answer any questions that may arise.

All DHCWs and patient participants will review and electronically sign the informed consent document prior to any study-related assessments or procedures. For LAB and POC patient subjects, an electronic consent and signature will be obtained before the Pre-Visit-Triage survey is completed.

Participants will be given the opportunity to discuss the study with their surrogates or think about it prior to agreeing to participate. They may withdraw consent at any time throughout the course of the study. A copy of the signed informed consent document will be given to participants for their records. The rights and welfare of the participants will be protected by emphasizing to them that the quality of their clinical care will not be adversely affected if they decline to participate in this study.

The consent process will be documented in the clinical or research record.

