15.6 Protocol Deviations

A protocol deviation is any change, divergence, or departure from the study design or procedures of a research protocol that is under the investigator's control and that has not been approved by the sIRB. Since the purpose of this feasibility study is for protocol refinement, any of the following will not be considered protocol violations unless the subject was put at additional risk as a result of the divergence from the protocol.

- Incomplete visits
- Activities occurring outside of the specified windows
- Missing surveys/forms or data

Upon discovery of a protocol deviation, the Principal Investigator is responsible for reporting protocol deviations to the sIRB.

A protocol violation is a deviation from the sIRB approved protocol that may affect the subject's rights, safety, or well-being and/or the completeness, accuracy and reliability of the study data. Protocol Violations must be submitted for Full Board sIRB review. If the deviation meets any of the following criteria, it is considered a protocol violation.

All deviations and violations from the protocol will be recorded on the Protocol Deviation/Violation Reporting Form no later than 10 business days after study staff become aware of the deviation and

forwarded to the study PI for review and reported promptly to the sIRB. All protocol deviations and violations will be reviewed monthly during the PREDICT Steering Committee Meeting.

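### The only scheduled consent-completeness review comes after study tests, the Section 6.1 consent window for dental staff conflicts with Sections 7 and 14.3, and the deviation exemptions do not exclude consent

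*Combined protocol and SAP*

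**What the plan says.** Section 14.3 sets the governing rule: all DHCWs and patients must "electronically sign the informed consent document prior to any study-related assessments or procedures". Section 5.1 makes a signed and dated consent an inclusion criterion.

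Four other places bear on how that rule works in practice.

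- **Completeness review (Section 13, Subject Completion Review).** "Consent forms will be reviewed for completeness at the mid-study visit for DHCW subjects and as part of the end-of-visit survey for patient subjects". No other review of consent forms is scheduled.
- **Consent timing for DHCWs.** The Section 6.1 tables for POC and LAB offices both put consent at Day -28 ± 29 days, with start of study on Day 0. Section 7 says "Within 4 weeks prior to study initiation in the dental office, the National Dental PBRN Node Coordinator will consent the DHCWs in the participating office", and labels the start-of-study visit Day 1. At that visit DHCWs are to "Complete two COVID-19 related tests".
- **Window outcome (Section 3.0).** The share of activities falling inside their defined window is a feasibility outcome, and consents are the first activity listed.
- **Exemptions.** Section 8.1.3 says "activities taking place outside of a specified window will not be considered a protocol deviation or violation", and treats missed or incomplete surveys and forms the same way. Section 15.6 says that incomplete visits, out-of-window activities and missing forms or data "will not be considered protocol violations unless the subject was put at additional risk as a result of the divergence from the protocol".

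**The concern.** A completeness review protects participants only if it comes before the procedures that depend on consent. Here a defective form would be found by the scheduled review only after a swab, saliva or tongue specimen and, for DHCWs, a finger prick. Those specimens and surveys might then have to be set aside, which matters in a study of at most 120 people.

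The consent window matters for a second reason: it defines what a feasibility outcome counts. If the window extends past the first tests, the outcome can record as on time a consent that breaches Section 14.3.

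The exemptions matter because they decide what is reported. Staff who find a late or incomplete consent would meet two rules that differ and do not mention consent. The study is meant to inform a network-wide application, so these rules could carry forward into it.

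**Working it through.** The plan states no figure to reproduce. The check compares windows (centre ± half-width) with test days, and counts tests.

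**1. Review against testing**

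- DHCWs: the mid-study visit is Day 14 ± 7 (Section 6.1), so 14 - 7 = Day 7 to 14 + 7 = Day 21. Start-of-study tests are on Day 0, so the review comes 7 to 21 days later (6 to 20 if the start is called Day 1).
- POC patients: swab at the start of the Day 1 visit, review with the end-of-visit survey. The review follows the swab.
- LAB patients: saliva at Day -7 ± 5, that is Day -12 to Day -2 (Section 6.2), review on Day 1. The review follows the specimen by days.

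**2. Tests before the participant's own scheduled review**

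- At target (Section 5.3: 40 DHCWs, 80 patients): 40 x 2 + 80 x 1 = 160.
- At the enlistment minimum in Section 5.3 (the dentist plus 4 other DHCWs, and 10 patients, in each of 4 offices): 4 x 5 x 2 + 4 x 10 = 80.

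**3. DHCW consent window**

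- Section 6.1: -28 - 29 = Day -57; -28 + 29 = Day +1.
- Section 7, with start on Day 0: Day -28 up to the start.
- Difference: 29 days at the early end and 1 day past the tests at the late end.
- With start called Day 1, the late end coincides with the test day, with no order stated. The early end is 1 + 57 = 58 days before start, against 28 in Section 7, a difference of 30 days.

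Renumbering can therefore remove the overrun past the test day, but not the early-end conflict.

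**4. Patient windows, for comparison**

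- POC: consent at Day -14 ± 14, that is Day -28 to Day 0, closing before the Day 1 swab.
- LAB: consent at Day -14 ± 7, that is Day -21 to Day -7. This overlaps the specimen window from Day -12 to Day -7. The windows alone do not force the order, but Section 7 lists receipt of the mailed kit after consent.

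**5. Exemptions side by side**

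| | Section 8.1.3 | Section 15.6 |
|---|---|---|
| Out-of-window activity is not | a deviation or a violation | a violation |
| Exception | none stated | additional risk to the subject |
| Consent excluded from the exemption | not stated | not stated |

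Section 15.6 and the Section 8.1 table also define a violation to include a deviation that may affect a subject's rights. A consent lapse bears chiefly on rights, so it could meet that definition without meeting the additional-risk exception.

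**The case against.** The strongest reply is that the protocol already prevents and detects the problem.

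- Sections 5.1 and 14.3 forbid testing without signed consent, and Section 7.1 puts DHCW consent before enrolment. A visit window does not authorise reversing that order.
- For patients, the pre-visit survey opens only once consent is completed, and LAB kits are listed after that step.
- Section 13 has the PI and the Chief of Clinical Protocol follow a REDCap dashboard and verify each instrument. Consents are documented in REDCap.
- Testing before signature breaches Section 14.3. It is more than an activity outside a window, so the exemption does not clearly reach it, and the rights-based definition of a violation would support reporting.
- The Day +1 end may be only a mismatch between Day 0 and Day 1 numbering.

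Much of this stands. A reader might infer that tests without valid consent are neither prevented nor flagged; for the reasons just listed, the documents do not support that.

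It does not dispose of the narrower point. The dashboard text does not name consent forms, gives no timing relative to testing and does not block a test. Section 13 lets subjects save forms with responses missing. The patient step controls the survey and is not said to control specimen collection. No equivalent step is stated for DHCWs. Section 10 provides no outside monitoring. The numbering explanation leaves the early-end conflict in place, and the difference between Sections 8.1.3 and 15.6 is on the page.

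**Conclusion.** The point holds in this form. The scheduled consent review comes after testing for every group, and the gap is clearest for DHCWs. The Section 6.1 window conflicts with Section 7 at both ends on Day 0 numbering, and its Day +1 end also conflicts with Section 14.3. The Section 3.0 outcome can therefore count as on time a consent signed after the Day 0 tests, or more than four weeks before them. Sections 8.1.3 and 15.6 disagree, and neither says that consent is outside the exemption.

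The size is up to 160 tests before the scheduled review at target enrolment, or 80 at the enlistment minimum. These count tests that precede the review. They do not count people tested without valid consent. A reader might be tempted to apply an error rate to obtain such a number, but the documents give no rate of incomplete consents, and an incomplete form is not necessarily an unsigned one.

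The 7 to 21 days and the Day +1 end assume Section 6.1's Day 0 numbering. The correction should be made, because it changes stated rules at small cost.

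**What to change.** 1. **Section 13.** Have the person obtaining consent, or the practitioner, confirm in REDCap that the consent record is complete and signed before the first study procedure: for DHCWs before start-of-study testing, for POC patients before the swab, and for LAB patients before the saliva kit is mailed. A lock on the Testing form alone would act too late for LAB patients, who collect at home and whose results are entered after the laboratory reports (Section 15.2).
2. **Section 6.1.** Restate the DHCW consent window to agree with Section 7, close it before the first start-of-study procedure, and use one day numbering for that visit in both sections. The Section 3.0 outcome then counts only consents obtained in the right order.
3. **Sections 8.1.3 and 15.6.** Reconcile the two exemptions, and state that neither the window exemption nor the incomplete-form exemption covers consent.

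The cost is wording in four sections and one confirmation per participant, at most 40 + 80 = 120. The downside is that a participant with an incomplete form waits until it is completed. The aim of learning whether the other windows and forms are workable is unaffected.
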